## VI. Special precautions, including dose modifications

We will not make modifications of the vitamin D dose based on the study design. As described in Section XI, "Monitoring Subject Safety", subjects will be advised to cease vitamin D supplementation if specific lab values

## VII. Description of experimental controls and use of placebos

In this 2,000-person two-arm, double-blinded randomized controlled trial, we will randomize half the subjects to low dose vitamin D therapy (400 IU/day), which will serve as the control group, and half to moderate (4,000 IU/day) or high (10,000 IU/day). Participants will have the option of being randomized to the high versus low strategy or the moderate versus low strategy. The low dose was selected to ensure that all subjects had a high likelihood of a total vitamin D intake that met the recommended daily allowance (RDA).

## VIII. Type and number of experimental subjects

We plan to recruit 2,000 health care workers and other Chicagoland community members. HCWs will be primarily employed at the University of Chicago Medicine (UCM)- Hyde Park, River East, or Ingalls, and Rush University (RU) at the Rush University Medical Center, Rush Oak Park Hospital, and Rush South Loop clinics. At UCM, ~250 HCWs have been diagnosed with COVID-19 as of late June, out of a reduced pool working non-remotely of about 3,000 persons over 4 months, for a monthly incidence of about 2% of working HCWs per month. During the summer months, as COVID-19 rates declined and stabilized in Chicago, the monthly incidence at UCM has fallen to about 1% per working HCW per month, but this reflects continued closure of most ambulatory services, which are now among the highest risk services given COVID-19 testing of all inpatients but not outpatients. Indeed, our inpatient COVID-19 unit has reported zero HCW infections. Thus the relative odds of infection appear to be several times higher in high risk HCWs than low risk HCWs. In the presence of appropriate personal protective equipment, high risk HCW groups based on the UCM experience and the literature are persons working in high volume ambulatory settings (e.g., primary care, ophthalmology), the emergency department, radiology, respiratory services, nursing, patient transport, custodial and food services. We will prioritize recruitment of these groups, and since ambulatory care is rapidly reopening now, we think that 3% is a reasonable estimate for the baseline monthly incidence in our study subjects. We think this is a conservative estimate as it is similar to the rate in the general local population. As COVID-19 infection rates have spiked in Chicago and neighboring communities over the past few months, the vast majority HCWs who test positive report community exposure, predominantly from transmission in their household or from those in their close

social network. Further, since two COVID-19 vaccines are now available we will expand our population to also include Chicagoland community members, who continue to be at increased risk for COVID-19 infection, with increased rates from 15 to 70 per 100,000 in recent months, trust gaps in vaccines, and lower priority access to vaccines for many outside the health care/front line professions—all resulting in potential lower rates of vaccination among the general population and a continued risk of infection.

The sample size was chosen to have at least 80% power to detect a 25% or larger decrease in the hazard of developing COVID-19 between study arms at  $p<0.05$  assuming a 30% baseline COVID-19 incidence rate over the study period, in line with the 3% per month incidence cited above.

*Individuals are eligible to enroll in the study if they:*

1. Are 18 years or older.
2. Live or work in the Chicagoland area (Illinois counties: Cook, Lake, McHenry, DuPage, Kane, Kendall, Grundy, Will, and Kankakee; Indiana counties: Lake and Porter).
3. Are interested in vitamin D as a potential preventive measure against COVID-19 in which they self-administer a daily dose of vitamin D during the 9-month study period.
4. Are willing to attend the laboratory for drop-in appointments at UChicago Medicine, Ingalls Hospital, or Rush University Medical Center every 3 months at up to 4 time points over up to a 9-month period for blood draws measuring COVID-19 antibodies, calcium, vitamin D and PTH levels.
5. Are willing to complete self-report measures at up to 4 time points over the course of up to 9 months by completing a 15-minute survey at intake by telephone or via web and 10-minute web-based follow-up surveys.

*Individuals are excluded from the study if they:*

1. Report being pregnant, planning to become pregnant, and/or report breastfeeding during the study period.
2. Report a history of chronic kidney disease, including a history of abnormal GFR and/or creatinine.
3. Report a history of hyperparathyroidism.
4. Report a history of increased falls.
5. Report a history of hypercalcemia.
6. Report a history of gastrointestinal absorptive disorders, including having undergone bariatric surgery.
7. Report a history of kidney stones (1 in past year or 2 in lifetime).
8. Report already taking more than 400 IU of vitamin D daily as recommended by their health care provider, excluding multivitamins and excluding supplements that include vitamin D and calcium together, unless permission is received from the prescribing health care provider to participate. In this case, no more than 1,000 IU vitamin D may be taken daily in addition to the study medication and we would limit the subjects to participation in the low vs. moderate arm of the study, producing a maximum dose of 5,000 IU per day. We note that the NAM recommended a maximum dose of 4,000 IU per day without medical supervision based on evidence that 5,000 was safe and known uncertainty about the precision of dosing in 5,000 IU supplements available over the counter. However, since we are testing the dosage of our 4,000 IU supplements to high precision and these patients would be taking their original supplements with a labelled dose of 1,000 IU or less, we think that the combination of our 4,000 IU supplements and the patient's original supplement of up to 1,000 IU should not provide a maximum dose meaningfully above the 5,000 IU actual dose the NAM has considered safe for taking without medical supervision. We note further that we are measuring vitamin D levels and PTH in these patients regardless in this study. We do, however, have another study of vitamin D and COVID (IRB# 20-0847), in which we are not measuring these levels, for which it is more important to not substantially exceed NAM maximum level of 5,000 IU per day. The approach described here allows us to align the approach in these two studies.
9. Report taking D2.
10. Report a history of sarcoidosis.

11. Screen positive for hypercalcemia ( at UCM, defined as >10.4 mg/dL and at Rush, defined as >11.2 mg/dL) during the initial blood test.
12. Screen positive for hyperparathyroidism (PTH>85 pg/dL) during the initial blood test with calcium  $\geq 10$ mg/dL and normal levels of vitamin D ( $\geq 30$ ng/mL)
13. Have vitamin D levels of >100ng/mL at study start, or >250ng/mL during follow-up labs.
14. Are unwilling to provide blood samples during quarterly blood tests.
15. Are unwilling to take daily vitamin D.

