During the consent process, study participants will be able to choose between being randomized between the low versus high dose strategy or the low dose versus moderate dose strategy. Moderate and high dose treatment participants will be combined for analysis as described below. The moderate and high treatment doses were chosen with help from our clinical advisory committee because they are generally considered safe and potentially effective among persons who meet our inclusion criteria based on medical history and baseline laboratory values (normal calcium and PTH, and negative COVID-19 antibodies). The low dose was selected to ensure that all subjects had a high likelihood of a total vitamin D intake that met the recommended daily allowance (RDA). All patients will be informed of whether their baseline calcium and PTH are normal. Patients who are still eligible for study participation after initial testing will be asked prior to randomization whether they are still willing to participate to maximize retention and minimize dropout. After randomization, subjects will be instructed to pick up their 9-month supply of vitamin D at either UCMC or Rush University corresponding to their randomized, blinded dose. For those unable to pick up their bottles in-person, the UCM IDS pharmacy will mail the subject their bottle. We propose a 3 to 9-month study period, depending on when the subject was recruited, as described in the study timeline of Section IV. Subjects recruited after September 30th will participate in the intervention 6 months to align with study timeline and funding. Subjects enrolled between January 1, 2023 and March 31, 2023 will take the study drug until June 2023, so at least 3 and no more than 6 months. Chart review for subjects will occur for 12 months after the active intervention period has ended. This study timeline is further detailed in Tables 1-4 of Section IV in the currently approved protocol document. Adverse events, defined as hypercalcemia or unexplained increased falls in either study arm will prompt discontinuation of the study medication and further evaluation as reported in the monitoring section below.

[figure not shown]
On the advice of our Clinical Advisory Council faculty members, patients who test for PTH >85pg/dL but have calcium levels <10mg/dL and low vitamin D (<30ng/mL) will be eligible to continue in the study because those

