who have elevated PTH, but low vitamin D and normal calcium likely have secondary hyperparathyroidism due to low vitamin D levels. However, since there is some risk that the PTH elevation in these patients is not due to low vitamin D, but instead primary hyperparathyroidism, we will check their calcium levels 30 days after they begin vitamin D supplementation and will follow the referral algorithm in the protocol should their calcium level become abnormal. Given this, we plan to reach out to subjects who have been previously disqualified but now meet the inclusion criteria to continue in our study to see if they still would like to participate. If they would like to, we will dispense them their randomized dose of vitamin D and follow up with calcium testing in approximately one month. Our exclusion criteria has therefore been modified to exclude those with  $\text{PTH} > 85 \text{ pg/dL}$  but with calcium  $\geq 10 \text{ mg/dL}$  and normal levels of vitamin D ( $\geq 30 \text{ ng/mL}$ ).

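### Exclusion 12 joins its calcium and vitamin D conditions with AND where OR is needed, so Section VIII admits two groups with PTH above 85 that the stated exception does not cover

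*Combined protocol and SAP*

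**What the plan says.** **The exception.** The Summary in Section III says that patients with "PTH >85pg/dL but have calcium levels <10mg/dL and low vitamin D (<30ng/mL) will be eligible to continue in the study". The reason given is that those "who have elevated PTH, but low vitamin D and normal calcium likely have secondary hyperparathyroidism due to low vitamin D levels". The same paragraph accepts that there is "some risk that the PTH elevation in these patients is not due to low vitamin D, but instead primary hyperparathyroidism", and so the team will "check their calcium levels 30 days after they begin vitamin D supplementation".

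**The exclusion.** Exclusion 12 in Section VIII reads "Screen positive for hyperparathyroidism (PTH>85 pg/dL) during the initial blood test with calcium" of 10 mg/dL or more and vitamin D of 30 ng/mL or more. The Summary states the modified exclusion with the same two conditions, also joined by AND.

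**The rest of Section VIII.** Inclusions 1 to 5 set no laboratory limits. Exclusion 3 covers only a reported history of hyperparathyroidism. Exclusion 11 removes calcium above 10.4 mg/dL at UCM or above 11.2 at Rush. Exclusion 13 removes baseline vitamin D above 100 ng/mL.

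**Outside vitamin D.** For people taking more than 400 IU/day on a provider's recommendation, and with that provider's permission, exclusion 8 caps outside vitamin D at 1,000 IU/day and states a maximum of 5,000 IU/day in total. Section XIV lets participants keep supplements of up to 2,000 IU/day in total. Both places limit these people to the 400 versus 4,000 IU option.

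**The concern.** The exception rests on one clinical argument: if vitamin D is low and calcium is normal, the raised PTH is probably a response to low vitamin D. Even then the protocol is cautious enough to add an early calcium check. Section III (Procedures and Materials) gives the reason, naming primary hyperparathyroidism as a risk factor for vitamin D toxicity.

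An exclusion that implements this exception should remove everyone with PTH above 85 who does not meet both of its conditions. Exclusion 12 removes only those who fail both. A screener working from the Section VIII list would therefore enrol people with raised PTH and sufficient vitamin D. They could be assigned up to 10,000 IU/day, and the readable text does not give them the early check that the better-explained group receives. What is at stake is participant safety and consistent screening, not the validity of the efficacy comparison.

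**Working it through.** **PTH rules.** Write Ca for calcium (mg/dL) and D for vitamin D (ng/mL), and take only people with PTH above 85.

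- Exception (Section III, Summary): Ca < 10 AND D < 30.
- Its complement: NOT(Ca < 10 AND D < 30) = (Ca ≥ 10 OR D ≥ 30).
- Exclusion 12 as written: Ca ≥ 10 AND D ≥ 30.

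| Calcium | Vitamin D | Covered by the exception | Removed by exclusion 12 | Result under Section VIII |
|---|---|---|---|---|
| < 10 | < 30 | yes | no | admitted |
| ≥ 10 | ≥ 30 | no | yes | excluded |
| < 10 | ≥ 30 | no | no | admitted by default (group A) |
| ≥ 10 | < 30 | no | no | admitted by default (group B) |

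So the exception covers 1 of 4 cells, and the operative list admits 3 of 4. These are counts of cells, not of people.

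**Limits from the other exclusions.**

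- Group A: exclusion 13 removes D > 100, leaving Ca < 10 with D from 30 to 100.
- Group B: exclusion 11 removes high calcium, leaving D < 30 with Ca from 10.0 to 10.4 at UCM (10.4 − 10.0 = 0.4 wide) or 10.0 to 11.2 at Rush (11.2 − 10.0 = 1.2 wide). The wider Rush window follows from that site's higher stated limit and does not by itself show more risk.

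**Fit with the rationale.** Group A does not fit: by the protocol's own cut-off their vitamin D is not low, so it cannot account for the PTH. Group B fits in part: vitamin D is low and calcium is within the site's limit, but it is not below the 10 mg/dL that the exception requires.

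**Monitoring.** In the readable text the 30-day check is attached to the exception group and to recontacted people. For newly screened people in groups A and B the first scheduled calcium is at month 3. For those enrolled in March 2023 that draw is also the final one, and final labs measure calcium but not PTH.

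**Outside vitamin D.**

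- The plan's figure reproduces: 4,000 + 1,000 = 5,000 IU/day.
- Under the Section XIV cap: 4,000 + 2,000 = 6,000 IU/day, which is 1,000 above the stated maximum and 6,000 / 10,000 = 60% of the trial's own high dose.
- The two caps differ in scope. Exclusion 8 leaves out multivitamins and calcium combinations; Section XIV counts all supplements together. They contradict each other directly only for provider-recommended users on 1,001 to 2,000 IU/day.

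**The case against.** The best defence is that the exception says who may continue, not that nobody else may. On that reading the Section VIII list governs, and nobody is left without a status. This stands. A reader might infer that groups A and B are neither admitted nor excluded, but the documents do not support that: both meet inclusions 1 to 5, meet no exclusion, and are admitted. The fault is that the list admits people whom the stated rationale does not cover.

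A reader might also infer that both groups were plainly meant to stay out, because the Summary describes participants by "baseline laboratory values (normal calcium and PTH, and negative COVID-19 antibodies". That is weak evidence. The same section makes an exception to normal PTH, Section VIII has no antibody exclusion, and Section XVII re-invites people once disqualified for a positive antibody test.

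Nor do the documents show that the two wordings produce different recontact lists. The plan to contact people "previously disqualified but now meet the inclusion criteria" follows directly on the exception and is most naturally read as applying to that group. For those recontacted, the text adds that "we will dispense them their randomized dose of vitamin D and follow up with calcium testing in approximately one month".

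The safety backstops are real. Group A enters with calcium below 10. Reported hyperparathyroidism, hypercalcemia, kidney disease and kidney stones (one in the past year or two in a lifetime) are excluded. Calcium is measured at month 3, and hypercalcemic participants are told to stop. Two figures, one just before the PTH paragraph in the Summary and the PTH referral algorithm in Section XI, are not shown and may deal with these groups. If they do, the written criteria should still agree with them.

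On supplements, a reader might add 2,000 IU to the high dose and reach 12,000 IU/day. Section XIV does not support this: people above 2,000 IU are asked to drop the excess, and those at 2,000 IU or less are confined to the 400 versus 4,000 IU option. Section III also describes risks up to 10,000 IU/day as minimal, so the 6,000 IU/day case is a consistency error with little safety consequence.

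**Conclusion.** The point holds and should be fixed. As written, exclusion 12 is not the complement of the exception it implements, and Section VIII by default admits groups A and B. Group A is the stronger concern because the low-vitamin-D explanation is unavailable to it; whether to keep group B is a clinical choice that the protocol should make openly.

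The documents give no count of people with PTH above 85, so the number affected is unknown and could be near zero. The conclusion assumes that screeners apply the Section VIII list as written and that the unseen figures do not override it. Sample size, power and the primary comparison are unaffected. The supplement caps are a minor, separate inconsistency of 1,000 IU/day for a narrow group.

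**What to change.** 1. In both Section III (Summary) and exclusion 12, exclude PTH above 85 pg/dL unless calcium is below 10 mg/dL AND vitamin D is below 30 ng/mL; equivalently, exclude it when calcium is 10 or more OR vitamin D is 30 or more.
2. If the team wants to keep group B, admit it explicitly and extend the 30-day calcium check to it.
3. Confirm that the PTH referral algorithm in Section XI states the same rule.
4. Use one outside-supplement cap and one counting rule in exclusion 8 and Section XIV: 1,000 IU/day if the 5,000 IU/day maximum is kept, or 2,000 IU/day with the maximum restated as 6,000.

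The cost is a wording amendment, with matching consent text where these rules are repeated. Expect a few more screen failures among people with PTH above 85. A 1,000 IU cap would require some supplement users to cut back. No extra visits are needed unless group B is kept, in which case each such person needs one additional calcium test.

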### Procedures and Materials

Blood labs will be taken from subjects at intake, 3 months, 6 months and, if in the 9-month cohort, 9 months. If subjects are in the 2023 cohort (defined as recruited on or after January 1, 2023) blood labs will be taken from

subjects at intake, 3 months, and, if they are recruited in January or February 2023, they will have one final blood draw in June 2023. Labs for UCM subjects will be drawn at DCAM phlebotomy, River East phlebotomy, or Ingalls Hospital, depending on the location most convenient for the subject. Labs for Rush subjects will be drawn by [name] at his Rush lab.

Intake labs will measure baseline calcium and PTH levels, presence of COVID-19 antibodies, baseline vitamin D levels, and vitamin A levels. Where possible given constraints related to sample storage, analysis and available funding for free vitamin D measurement, vitamin D measurements will include free vitamin D levels measured by ELISA assay, as well as total vitamin D levels.

For Aim 7, Intake labs for UCM subjects will additionally measure vitamin D-binding protein (DBP), RAS components (Renin, Ang II, soluble ACE and ACE2), bradykinin, inflammation markers (IL-6, TNF- $\alpha$ , IL-1 $\beta$  and CRP), and SARS-CoV-2 antibodies against S-protein and N-protein.

Follow-up labs (excluding the final lab) will measure PTH levels, calcium levels, vitamin A levels for those who have high baseline vitamin A, and vitamin D levels for monitoring of the intervention's safety and outcomes, and COVID-19 antibodies for monitoring of the outcome. Records of these levels will be kept by the UCM and RU PIs and laboratories.

Final labs will measure calcium levels, vitamin D levels for monitoring of the intervention's safety and outcomes, and COVID-19 antibodies for monitoring of the outcome. Records of these levels will be kept by the UCM and RU PIs and laboratories. Final labs will not measure PTH levels. During the intervention period, our study monitors PTH levels for active participants, because primary hyperparathyroidism is a risk factor for vitamin D toxicity. Given that participants will no longer be taking study-provided vitamin D after their final lab draw, we do not believe it is medically necessary or an appropriate use of limited study resources to continue checking PTH levels with this final draw.

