If a potential subject says they are already taking a supplement or supplements that contains more than 2,000IU vitamin D in total, we will ask the subject to discontinue supplements in excess of 2,000IU during their time on the study supplement to keep the guidelines straightforward for participants and avoid any potential for overdose.

After consenting, subjects will be asked to visit the laboratory to obtain the initial blood test to screen for abnormal PTH and calcium levels, obtain baseline 25(OH) vitamin D levels, and determine the presence of COVID-19 antibodies. After the initial blood tests, to improve compliance with vitamin D supplementation and screen for patients who may only be interested in joining the study to obtain baseline labs / antibody levels, subjects will be called and offered the opportunity to withdraw from the study after initial lab results are available, prior to randomization. We will also tell subjects about their other lab results if they suggest a safety concern and are outside normal ranges outlined in the exclusion criteria. If potential subjects have declined to withdraw at this initial stage, we will proceed with randomization.

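### The PTH cutoff is written as 85 pg/dL, which is 0.85 pg/mL; unless normal PTH reaches below that value, it cannot identify elevated PTH, and the unit is very probably a slip for pg/mL

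*Combined protocol and SAP*

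**What the plan says.** The PTH cutoff appears three times in the readable text, each time as 85 pg/dL.

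- Section VIII, exclusion criterion 12: "Screen positive for hyperparathyroidism (PTH>85 pg/dL) during the initial blood test". The person must also have calcium of at least 10 mg/dL and vitamin D of at least 30 ng/mL.
- Section III, Summary, on who may stay in: "patients who test for PTH >85pg/dL but have calcium levels <10mg/dL and low vitamin D (<30ng/mL) will be eligible to continue".
- Section III, Summary, at the end of the same explanation: "Our exclusion criteria has therefore been modified to exclude those with", followed by the same PTH value with the calcium and vitamin D conditions of criterion 12.

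The purpose of the cutoff is also stated. The Summary says that the people allowed to continue "have elevated PTH, but low vitamin D and normal calcium likely have secondary hyperparathyroidism due to low vitamin D levels". Because some of them might instead have primary hyperparathyroidism, the plan adds a safeguard: "we will check their calcium levels 30 days after they begin vitamin D supplementation". Section XIV describes the first laboratory visit as one to "obtain the initial blood test to screen for abnormal PTH and calcium levels".

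No readable section gives a numeric PTH reference range or states the cutoff in pg/mL. The PTH referral algorithm for the two sites is a figure that is not shown.

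**The concern.** A cutoff for elevated PTH has to lie at or above the upper end of normal values. Converted to pg/mL, the written cutoff is below one unit. If normal values lie above that, the PTH condition is met by essentially everyone who is tested and separates no one.

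The cutoff governs one exclusion criterion and one extra safety test, and two sites apply it. Under Procedures and Materials the plan explains that PTH is followed because primary hyperparathyroidism raises the risk of vitamin D toxicity, and some participants take 10,000 IU/day. If staff used 85 pg/mL while the protocol says 85 pg/dL, some enrolled participants would be ineligible on paper and some would lack a check that the text requires. Anyone who reuses the protocol would copy a cutoff that does not work.

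**Working it through.** **Inputs.** From the documents: PTH above 85 pg/dL (criterion 12, and twice in the Section III Summary); calcium cut at 10 mg/dL and vitamin D at 30 ng/mL (same places); hypercalcemia limits in criterion 11 of above 10.4 mg/dL at UCM and above 11.2 mg/dL at Rush. Assumed, because the documents give no figure: the lower and upper limits of normal PTH.

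**Step 1: conversion.** 1 dL = 100 mL, so 85 pg/dL = 85/100 = 0.85 pg/mL. In the other direction, 85 pg/mL = 85 × 100 = 8,500 pg/dL. The two readings differ by a factor of 100.

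**Step 2: comparison with assumed normal limits.** Ratio = assumed limit / 0.85.

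| Assumed limit of normal PTH (pg/mL) | Ratio to the written cutoff |
|---|---|
| lower limit 1 | 1.2 |
| lower limit 5 | 5.9 |
| lower limit 10 | 11.8 |
| lower limit 18 | 21.2 |
| upper limit 50 | 58.8 |
| upper limit 65 | 76.5 |
| upper limit 85 | 100 |

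The written cutoff lies below every assumed lower limit, including 1 pg/mL. The conclusion would fail only if a material share of screened adults had PTH at or below 0.85 pg/mL.

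**Step 3: what the two rules become when PTH is always above the cutoff.**

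| Rule | Cutoff of 85 pg/mL | Cutoff of 85 pg/dL, read literally |
|---|---|---|
| Criterion 12 excludes | PTH >85 pg/mL with calcium ≥10 mg/dL and vitamin D ≥30 ng/mL | everyone with calcium ≥10 mg/dL and vitamin D ≥30 ng/mL |
| 30-day calcium check | PTH >85 pg/mL with calcium <10 mg/dL and vitamin D <30 ng/mL | everyone with calcium <10 mg/dL and vitamin D <30 ng/mL |

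**Step 4: fit with the rest of the plan.**

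- Criterion 11 accepts calcium up to 10.4 mg/dL at UCM and 11.2 mg/dL at Rush. Literal criterion 12 would exclude people with vitamin D ≥30 ng/mL whose calcium is 10.0 to 10.4 mg/dL at UCM or 10.0 to 11.2 mg/dL at Rush. For them the site-specific limits would have no function.
- The routine schedule is "Blood labs will be taken from subjects at intake, 3 months, 6 months and, if in the 9-month cohort, 9 months". It has no 30-day draw, so the check is written as an exception for a small-risk group. Literally, it would become standard for everyone with low vitamin D and calcium below 10 mg/dL.

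**Step 5: direction.** Everyone above 85 pg/mL is also above 0.85 pg/mL. For these two rules, the literal reading can therefore only enlarge the excluded group and the monitored group.

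**The case against.** The strongest case on the other side has four parts.

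- **The plan is consistent with itself.** It uses one unit throughout and prints no reference range, so the error shows only with an assumption about normal PTH. This is true, and the conclusion is stated conditionally for that reason. The condition is weak: any lower limit above 0.85 pg/mL is enough.
- **The cutoff seems to have worked in practice.** The Section III Summary says that people disqualified earlier, who qualify under the relaxed rule, will be contacted again. The earlier threshold is not printed. If it was also 85, a working value of 0.85 pg/mL would have disqualified essentially everyone. This is indirect evidence that staff applied a cutoff that separated people, and it stands.
- **The missing figure may settle the unit.** The PTH referral algorithm could print pg/mL. Its absence from the readable text does not count against the plan.
- **Nothing statistical is wrong.** This is also true. No sample size, power or analysis figure depends on the cutoff.

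A reader might infer more than the documents support:

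- That the sites screened on the wrong value. The documents do not say which unit was applied, and the indirect evidence points the other way.
- That hyperparathyroidism was missed. Step 5 shows that the literal rules catch more people, not fewer. No claim is made about follow-up PTH or the algorithm that is not shown.
- That a count of extra draws or exclusions can be given. The documents contain no joint distribution of calcium and vitamin D in this population, so any count would rest on an invented share and on a reading that was very probably not intended.
- That people above the cutoff with high calcium and low vitamin D, or the reverse, are left without a rule. By default criterion 12 does not exclude them, criterion 11 still applies to their calcium, and the matter is the same under either unit.

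**Conclusion.** The point holds as a wording error in an eligibility and safety threshold. The stated cutoff is 0.85 pg/mL, 100 times below 85 pg/mL. With an assumed lower limit of normal of 5 to 18 pg/mL, it lies 5.9 to 21.2 times below that limit. As written, it cannot identify elevated PTH or a positive screen for hyperparathyroidism.

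This rests on one assumption from outside the documents, that normal PTH lies above 0.85 pg/mL. The intended unit is very probably pg/mL, though no readable text confirms it. The defect is therefore probably in the text rather than in the conduct of screening. Confidence is high for the wording slip; no operational consequence is established. Severity is minor.

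**What to change.** Ask the UCM and Rush laboratories in which unit they report PTH. If it is pg/mL, replace pg/dL with pg/mL in exclusion criterion 12 and in the two places in the Section III Summary, and in the PTH referral algorithm if it carries the same unit. Add a sentence stating which unit was applied at screening, so that records can be compared with the protocol.

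The cost is one query to each of two laboratories, a one-word change in three or four places, and that sentence. No design, sample size or analysis text changes.
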